5.9.3 Management of ocular toxicities

As described in Section 2.2.8, preclinical studies noted evidence of Fc γ RIIB expression on the eye. Eye examinations have therefore been included in the schedule of events to allow for assessment throughout study treatment.

If any grade of toxicity affecting the macula and/or affecting patient's vision is observed then study treatment must be stopped and intensified monitoring implemented as per the site ophthalmologist's recommendation. Restarting treatment will be considered on discussion with the PI, CI, ophthalmologist and Sponsor.

If NCI-CTCAE v4.02 Grade 1 ocular toxicity is observed which does not affect the macula or patient's vision, study treatment may continue with intensive monitoring as per site ophthalmologist's recommendation.

If Grade 2 or above ocular toxicity is observed, not affecting the macula or patient's vision, treatment must be stopped and intensified monitoring should be implemented as per site ophthalmologist's recommendation. Restarting treatment will be considered on discussion with the PI/CI, ophthalmologist and Sponsor

5.9.4 Management of thrombocytopenia (Grade 4)

If Grade 4 thrombocytopenia is noted post infusion:

- Perform daily (or as frequent as possible) full blood count (FBC) monitoring until resolution to Grade 3 or less.

- If this is not possible, then the patient should be monitored closely until resolution to Grade 3 or less AND as a minimum a FBC must be performed on the 5th day from when Grade 4 thrombocytopenia was first noted (unless there is documented resolution to Grade 3 before that point).
- Toxicity must be resolved to at least Grade 2 or lower before the next dose can commence; therefore a delay in treatment may be required.

5.9.5 Dose reductions

Patients who experience a DLT (as defined in [Section 3.3](#)) that resolves to Grade ≤ 1 or recovers to baseline within 7 days of the start of the DLT may recommence treatment (with BI-1206 \pm rituximab), with the agreement of the PI, CI and Sponsor. The dose should be reduced to the previous dose level and rate of infusion may be reduced and agreed with the Sponsor and Investigator prior to treatment.

If the AE has not resolved to Grade ≤ 1 or recovered to baseline within 7 days, the patient will be taken off-study and treatment should be discontinued. If the patient experiences another DLT, either the same or different toxicity, further treatment is not permitted.

5.9.6 Dose delays and Treatment Discontinuation

In this trial, if a patient experiences one or more of the following toxicities related (highly probably, probably or possibly) to BI-1206 or rituximab treatment, the treatment for that patient should be delayed/modified as described. Please refer to Section 5.9.2 for actions to be taken in event of a reaction during the infusion.

Grade 1 or 2 toxicity (haematological or non-haematological) other than ocular toxicity or infusion related reaction.

No dose modifications or delays are necessary; refer to Section 5.9.3 for guidance on management of ocular toxicity, Section 5.9.2 for guidance on management of infusion related reactions.

Grade 3 or 4 Haematological toxicity that does not meet DLT definition as described in Section 3.3

Treatment with BI-1206 and rituximab, if applicable should be delayed until recovery of the patient's full blood count to Grade ≤ 2 . Treatment may be delayed for a maximum of three weeks. Patients experiencing \geq Grade 3 haematological toxicity lasting longer than three weeks must not receive further treatment with BI-1206 or rituximab. Growth factor support is permissible during this period.

Grade 3 or 4 Non-haematological toxicity that does not meet DLT definition as described in Section 3.3

Refer to Section 5.9.3 for guidance on management of ocular toxicity, Section 5.9.2 for guidance on management of infusion related reactions. For other events, treatment with BI-1206 and rituximab, if applicable, should be delayed until recovery of the AE(s) to Grade ≤ 2 . Treatment may be delayed for a maximum of three weeks. Patients experiencing \geq Grade 3 toxicity lasting longer than three weeks must not receive further treatment with BI-1206 or rituximab.

Please see [Sections 6.2.5.6](#) and [6.2.11.2](#) for further information relating to patient withdrawal from treatment.

Modifications for logistical reasons i.e. Bank Holidays

For logistical reasons (i.e. bank holidays), treatment may be delayed by a maximum of one week or treatment may be given one day earlier (decrease time between dosing to six days during induction therapy) following agreement by CI and Sponsor, prior to commencing treatment.

5.9.7 Duration of treatment

In the induction phase, treatment should continue for four weeks unless (a) the patient asks to be withdrawn, (b) there is evidence of disease progression, (c) the patient is experiencing unacceptable toxicity or (d) the Investigator feels the patient should be withdrawn for any other reason. Other reasons are listed in Section 11.

The duration of treatment may be extended if dose interruptions/ delays result in an extended induction period.

5.9.8 Maintenance therapy

Patients who are deriving clinical benefit (as defined in Section 10.2) may continue at the end of the induction therapy onto maintenance therapy for up to 1 year following their first dose of BI-1206 treatment on the study. Maintenance therapy will cease if (a) the patient asks to be withdrawn, (b) there is evidence of disease progression, (c) the patient is experiencing unacceptable toxicity or (d) the investigator feels the patient should be withdrawn for any other reason. Other reasons are listed in Section 11. As BI-1206 is at an early stage of development, the long term side-effects are unknown. Treatment will therefore not continue beyond the one year maintenance period of this study.

5.9.9 Replacement of patients

Patients who come off study due to dose limiting toxicity prior to completing four weeks of induction therapy will not be replaced. Patients who come off study prior to completing four weeks of induction therapy for any other reason will be replaced for purposes of DLT evaluation during the single and combination dose escalation cohorts. Once a RP2D dose has been established (BI-1206 monotherapy and BI-1206 + rituximab combination) patients who withdraw due to disease progression and/or unacceptable toxicity will not be replaced. Other withdrawn patients may be replaced, if considered appropriate, after discussion between the PI, CI and Sponsor.

There may be circumstances based on the emerging data from the trial or IMP availability which result in a patient not being replaced. This will be documented by the Sponsor.

5.10 Concomitant medication and treatment

Concomitant medication may be given as medically indicated. Details of the concomitant medication given must be recorded in the patient's medical records and the electronic case report form (eCRF).

Radiotherapy may be given concomitantly for the symptomatic control of lymphadenopathy; however these irradiated lesions will not be evaluable for response.

Refer to Section 5.9.2 for details of pre-medications to be administered prior to BI-1206 and/or rituximab infusions. Live vaccinations are not permitted whilst on the trial; other immunisations are permitted. Doses of prednisolone >10 mg daily (or equipotent doses of other corticosteroids) are not permitted whilst on the trial, other than as pre-medication where the patient is at risk of tumour lysis due to high tumour burden, where it has been approved by the CI and Sponsor as an alternative pre-medication or if alternative steroids are required, if clinically indicated to treat infusion related reactions as per Section 5.9.2. During the screening period, doses of up to 20mg per day may be given but the dose must be reduced to 10mg/day by Week 1 Day 1 (other than as pre-medication).

The patient must not receive any other anti-cancer therapy or investigational drugs while on the trial. Participation in an observational study is allowed.

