3.5 Patient evaluability

3.5.1 Response

All patients who meet the eligibility criteria, receive at least one administration of mAb (BI-1206 with/without rituximab) as part of this trial, have a baseline assessment of disease and at least one repeat disease assessment will be evaluable for response.

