9.6.3 Eligible patients

For eligible patients, SAE and AE collection and monitoring will commence at the time the patient gives their written consent to participate in the trial by signing the main study consent form and will continue until 125 days after the last administration of BI-1206 and/or rituximab on study (whichever is later) or until the patient starts another anti-cancer therapy.

Should an Investigator become aware of any drug-related SAEs after this 125 day period (even if the patient has started another anti-cancer therapy), these must also be reported to the CDD within the expedited timelines in Section 9.7.

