- Bone marrow aspirate and biopsy for patients who had a positive test at baseline and who have shown a complete response and who have not had prior bone marrow confirmation of response.

All lesions measured at baseline must be measured at every subsequent disease assessment, and recorded clearly on the scan reports. All non-measurable lesions noted at baseline must be noted on the scan report as present or absent.

All patients, who are removed from the trial for reasons other than progressive disease, must be re-evaluated at the time of treatment discontinuation, unless a tumour assessment was performed within the previous four weeks.

It is the responsibility of the Principal Investigator to ensure that the radiologists are aware of the requirement to follow-up and measure every target lesion mentioned at baseline and comment on the non-target lesions in accordance with Hallek criteria (Appendix 5).

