13.5 Anti-tumour activity

Documenting anti-tumour activity is a secondary objective of this trial. Patients must receive at least one dose of BI-1206 and/or rituximab on as part of this trial; have a baseline disease assessment and at least one follow-up disease assessment to be evaluable for response. Patients who experience clear clinical disease progression without formal post-treatment disease assessment will be included and will be considered to have progressive disease. Objective responses, the best tumour response achieved by each patient while on trial and the time to progression will be presented in the data listings.

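### Section 5.10 drops a node irradiated on trial from the response assessment but sets no patient-level rule, so best response and PFS may read too favourably

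*Combined protocol and SAP*

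**What the plan says.** Section 5.10 allows radiotherapy during the trial and states its consequence at lesion level: "Radiotherapy may be given concomitantly for the symptomatic control of lymphadenopathy; however these irradiated lesions will not be evaluable for response". The same section then says: "The patient must not receive any other anti-cancer therapy or investigational drugs while on the trial".

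Evaluability for response is defined at patient level, without reference to radiotherapy. Section 3.5.1 requires that eligible, dosed patients "have a baseline assessment of disease and at least one repeat disease assessment will be evaluable for response". Section 10.4 repeats this, and Section 13.5 asks that patients "have a baseline disease assessment and at least one follow-up disease assessment to be evaluable for response". Section 13.5 adds one rule for clinical progression: "Patients who experience clear clinical disease progression without formal post-treatment disease assessment will be included and will be considered to have progressive disease". It then lists "the best tumour response achieved by each patient while on trial".

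Section 13.6.2 keeps patients in the PFS analysis whatever treatment follows and does not censor at a new treatment. It does not make new treatment an event either. Under Section 10.3, disease is assessed at baseline, at Week 8, every 16 weeks in maintenance and at off-study, or earlier if progression occurs. Section 10.3.1 requires: "All lesions measured at baseline must be measured at every subsequent disease assessment, and recorded clearly on the scan reports".

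Under Sections 7.5.1 and 9.6.3, AE collection runs to 125 days after the last dose or "until the patient starts another anti-cancer therapy".

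**The concern.** Leaving an irradiated node out of the response score is sound in itself, because it stops shrinkage caused by radiotherapy being credited to BI-1206. The gap is that nothing is said about the patient. A node that needs radiotherapy for symptoms may well be one that has not responded. If it leaves the score and nothing else changes, the patient is judged on the lesions that did better.

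Best response and PFS are secondary endpoints in arms with no concurrent control, so no comparison would absorb such a bias. The trial is also open label. Without a written rule, each case would be settled by someone who knows the patient's course.

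**Working it through.** The plan gives no figure on this point to reproduce. The check sets the rules side by side and then illustrates their effect with assumed lesion sizes.

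**1. Is the patient removed or reclassified?** No. Sections 3.5.1, 10.4 and 13.5 need only a dose, a baseline and a repeat assessment. The clinical-progression rule in 13.5 covers only patients with no formal post-treatment assessment, so a patient with a Week 8 scan falls outside it. Inclusion criterion 8 asks most lymphoma patients for only one measurable lesion. If that lesion is irradiated, the patient stays evaluable with no measurable lesion to score.

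**2. Effect on response (lymphoma, CT criteria, Appendix 5).** PR needs at least a 50% fall in the summed products (SPD) of the target lesions. Let f be the irradiated node's share of baseline SPD, g its growth before radiotherapy, and s the shrinkage of the other lesions.

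All-lesion change = (1 − f)(1 − s) + f(1 + g) − 1.

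Assume s = 0.55, so the remaining lesions alone give −55%, which is PR. Take g = 0 (unchanged) or g = 0.40 (below the 50% growth required for PD on a single node).

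| f | g = 0 | g = 0.40 |
|---|---|---|
| 0.20 | 0.36 + 0.20 − 1 = −44% | 0.36 + 0.28 − 1 = −36% |
| 0.40 | 0.27 + 0.40 − 1 = −33% | 0.27 + 0.56 − 1 = −17% |
| 0.60 | 0.18 + 0.60 − 1 = −22% | 0.18 + 0.84 − 1 = +2% |

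All six are SD on all lesions and PR once the node is dropped.

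**3. Other diseases.** In CLL (Appendix 4), PR needs two group A criteria and one group B criterion, and nodes are only one of the group A criteria. In Waldenström's macroglobulinaemia (Appendix 6), categories rest largely on IgM. The effect should be weaker in both.

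**4. Effect on PFS.** No assessment is required before or because of radiotherapy. In maintenance, a node can enlarge after one CT, be irradiated, and be smaller at the next CT 16 weeks later. Section 13.6.2 then records neither an event nor censoring, and PFS continues.

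**5. Weight of one patient.** In an expansion arm of 25, 1/25 = 4.0 points. This is the weight of any single patient. It is not an estimate of the bias, because the documents do not say how often radiotherapy is expected.

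**The case against.** Four stronger readings are tempting, and the documents do not support them.

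- **A reader might infer that failure at an irradiated site can never count as progression.** Section 5.10 says the lesion is not evaluable for response; it does not remove it from the PD criteria. Appendix 4 calls PD on growth at any previous site and Appendix 5 on an individual node. Section 10.3 brings the evaluation forward when progression occurs early. A node that met PD at a scan before radiotherapy should still count. What remains is growth that nobody measured first.
- **A reader might infer that the error can only be favourable.** A symptomatic node may be stable, or may be shrinking on drug, and dropping a shrinking node can lower the apparent response. The documents do not say which nodes would be irradiated.
- **A reader might see a conflict with the measurement rule in 10.3.1.** A lesion can be measured and recorded without being scored. The rule in fact preserves the data needed for the fix.
- **A reader might infer that the primary safety endpoint is affected, because AE collection could stop at radiotherapy.** Sections 7.2 and 7.3 separately require AE assessment before each BI-1206 administration, and drug-related SAEs remain reportable under 9.6.3 after another therapy starts. That removes most of the claim; only an ambiguity of wording is left.

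The bar on other anti-cancer therapy in 5.10 can also be read as a general rule to which the radiotherapy sentence is the exception. That is a natural reading, but the text does not state it, and exclusion criterion 6 lists radiotherapy beside chemotherapy and immunotherapy.

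Finally, Section 13.5 places responses in data listings and plans no response-rate estimate, and no decision rule uses response or PFS. This limits the weight of the point, but the listed category can still be wrong.

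**Conclusion.** The concern holds as a missing patient-level rule. Applied as written, Section 5.10 lets a patient whose irradiated node had not responded be listed as PR instead of SD, and lets unmeasured growth between scans go uncounted in PFS. The response half follows directly from the text. The PFS half follows from its silence.

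The illustration assumes that the irradiated node was a target lesion, that 5.10 is applied literally, and that the other lesions met PR by themselves. The likely direction is favourable, though not in every case. If a response rate is reported, one patient is worth 4.0 points in an arm of 25. The total effect cannot be sized, because the frequency of on-trial radiotherapy is not given. Only descriptive secondary endpoints are touched, so this is an inexpensive improvement worth making before analysis. It does not threaten the trial's main conclusions.

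**What to change.** In Sections 10.4, 13.5 and 13.6.2:

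1. State that an irradiated lesion still counts for PD on any measurement taken before radiotherapy.
2. In the main listing, do not credit a CR or PR first seen after on-trial radiotherapy; take best response from earlier assessments. Keep a patient with no earlier post-baseline assessment in the denominator as a non-responder. Flag any later response at non-irradiated sites separately.
3. Add one PFS sensitivity analysis with on-trial radiotherapy as an event.

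The denominator clause in item 2 matters. For a node irradiated before Week 8, the last scheduled CT is baseline. If such a patient became non-evaluable, an assumed 6/25 = 24% would rise to 6/24 = 25%, so the correction would itself favour the drug.

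Separately, the radiotherapy permission in 5.10 must be reconciled with the bar on other anti-cancer therapy in that section and with the AE-collection stop in 7.5.1 and 9.6.3. Which clinical rule should apply is for the sponsor and investigators.

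The cost is wording and one extra analysis, with no new scans. The downside is that genuine later responses at other sites move to the flagged listing, and response and PFS may look slightly less favourable.

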6 PHARMACEUTICAL INFORMATION

6.1 Supply of BI-1206 and rituximab

6.1.1 Supply of BI-1206

A complete certificate of analysis and a Qualified Person (QP) certification must be provided with each batch of the investigational medicinal product (IMP): BI-1206 and be retained in the Pharmacy File.

For information on BI-1206 and re-ordering of supplies, contact the Clinical Research Associate (CRA)/Clinical Study Manager (CSM) responsible for the trial who will arrange further supplies.

BI-1206 will be manufactured by:

Nova Laboratories Limited

[REDACTED]

BI-1206 will be stored, labelled and distributed by:

Cancer Research UK Formulation Unit

[REDACTED]

The distributor (Cancer Research UK Formulation Unit) must provide confirmation of the shipment to the CSM/CRA on despatch of the IMP.

The primary and secondary packaging for the IMP will be labelled according to Eudralex Volume 4: Annex 13 'Investigational Medicinal Products' of the European Union guide to Good Manufacturing Practice (GMP).

Prior to despatch of BI-1206 to the clinical trial site a label detailing the Investigator's name and site name and address will be added by the Manufacturing Authorisation Holder in accordance with GMP to the secondary packaging (box).

An example of the approved label(s) can be found in the TMF and site Pharmacy File.

6.1.2 Supply of rituximab

Rituximab will be considered an IMP as patients will not be taking the drug before enrolment on this trial. Rituximab is licensed for clinical use in the UK and EU and is marketed under several different brand names and will be used in accordance with the respective SmPC. The investigators will be responsible for their own supply of rituximab. Prior to dispensing rituximab will be labelled by the Pharmacy according to Eudralex Volume 4: Annex 13 'Investigational Medicinal Products' of the EU Guide to Good Manufacturing Practice. The label applied by Pharmacy will be approved by CR-UK and an example of the approved label for rituximab will be filed in the Pharmacy Folder. Sufficient quantities of rituximab will be dispensed to cover the prescribed dose (as per Section 6.2).

Rituximab will be dispensed from the hospital pharmacy on a per patient basis.

As per Section 2.2.7, it should be noted rituximab biosimilars may be used in this clinical trial (**Sponsor must be notified prior use**). For additional information concerning rituximab, please refer to the SmPC specific to the brand used. Note the rituximab SmPC included in the IB Package supplied to the support the current clinical trial will be used as the RSI for rituximab in this trial.

6.2 Pharmaceutical data

6.2.1 Formulation of BI-1206

BI-1206 will be supplied as a concentrate for solution for infusion (5mL fill volume) in 5 mL Type 1 clear glass vials with a concentration of 10 mg/mL. [REDACTED]

6.2.2 BI-1206 storage conditions

All supplies must be stored in a secure, limited access storage area.

BI-1206 must be stored in its original packaging at 2-8°C, protected from light.

6.2.3 Method of preparation of BI-1206 for administration

Good aseptic practice must be employed when preparing solutions of BI-1206 for infusion.

[REDACTED]

[REDACTED]

[REDACTED]

[REDACTED]

[REDACTED]

Please refer to the Pharmacy and Drug Administration guidelines located in the Pharmacy File for additional guidance.

Each vial of BI-1206 is for single use only. Any unused contents and/or vials dispensed for patient use must be destroyed as per local policies and accounted for as described in Section 6.3.1.

6.2.4 Stability and labelling of the diluted BI-1206

After removal from the refrigerator and dilution [REDACTED], BI-1206 solution can be kept at ambient temperature. From a microbiological point of view, the administration should be performed as close as possible to the preparation of the diluted drug. For the 0.4mg dose level the diluted drug must be administered within 24 hours of dilution. For all other dose levels (2mg upwards) the diluted drug must be used within 48 hours of dilution. Refer to the handling instructions in the Pharmacy File for further details. Labelling requirements for the reconstituted BI-1206 for infusion can be found in the Pharmacy File.

6.2.5 BI-1206 administration

Before administration, the exact dosage must always be double-checked by a second suitably qualified person. All checks and double-checks must be documented (signed and dated) and the documentation must be available for the CRA/CSM to verify.

